### **6.3. Potential Risks and Benefits**

Although the clinical case report data is extremely encouraging, the true response rate to GM-CSF in NTM infection is unknown. This pilot study is intended to gather the detailed data relevant to planning of the further phase II program, to be conducted in the more formal setting of a randomized, double-blind clinical trial.

As outlined above, pulmonary NTM disease is now a major problem and is increasing, treatment is poorly tolerated, is often ineffective and even successful therapy is associated with recurrence rates of 50% within 3 years. Patients urgently need better therapies.

As the majority of inhalational use of rhGM-CSF has been in the context of PAP, where patients have pre-existing anti-GM-CSF antibodies, it cannot be excluded that there will be more adverse effects in the treatment of NTM infection due to higher local and systemic exposure. The safety monitoring in the study has been selected to address these aspects.

To ensure adequate subject safety in this pilot study, a data review was conducted by a review committee (the lead investigators and sponsor representatives) after the first 6 subjects had completed 12 weeks treatment as outlined above. This might result in reduced dosing frequency if there were safety concerns or poor tolerability. Overall, the safety profile was concluded to be acceptable and the committee endorsed continuation of the trial using the same dose, and extension of the treatment duration to 48 weeks. Recruitment beyond the 6 first subjects was not stopped during the review period. If needed, unscheduled visits will be conducted at investigator's discretion.

The trial will be conducted in compliance with the protocol, all applicable regulatory requirements, good clinical practice (GCP) and the ethical principles of the latest revision of the Declaration of Helsinki as adopted by the World Medical Association.

Overall, there is a good chance for study subjects to gain improvement from their condition through participation in the study and the study will, if successful, be an important step on the path to an approved treatment for pulmonary NTM infection.

## **7. TRIAL OBJECTIVES AND PURPOSE**

### **7.1. Primary Objective**

The primary objective is:

- To investigate efficacy of inhaled molgramostim on NTM sputum culture conversion to negative.

### **7.2. Secondary Objectives**

The secondary objectives are:

- To investigate efficacy of inhaled molgramostim on NTM sputum smear conversion to negative.
- To investigate efficacy of inhaled molgramostim on reduction of NTM bacterial load in sputum.
- To investigate efficacy of inhaled molgramostim on exercise capacity.
- To investigate efficacy of inhaled molgramostim on Patient Reported Outcomes.
- To investigate safety of inhaled molgramostim in subjects with NTM infection.

### **7.3. Endpoints**

#### **7.3.1. Efficacy Endpoints**

##### **7.3.1.1. Primary Efficacy Endpoint:**

- Sputum culture conversion defined as at least three consecutive negative sputum samples during the treatment period.

##### **7.3.1.2. Secondary Efficacy Endpoints:**

- Sputum smear conversion defined as at least three consecutive negative AFB stained sputum smears on microscopy during the treatment period in subjects who were smear positive at Baseline.
- Durability of sputum culture conversion (defined as conversion at or before Week 48 and culture still negative at 12-weeks follow-up).
- Durability of sputum smear conversion (defined as conversion at or before Week 48 and smear still negative at 12-weeks follow-up).
- Change in semi-quantitative grade of number of NTM on microscopy of AFB stained sputum smears from Baseline to Weeks 4, 8, 12, 16, 20, 24, 28, 32, 36, 40, 44, 48 and 12-week follow-up.
- Change in semi-quantitative grade of sputum cultures from Baseline to Weeks 4, 8, 12, 16, 20, 24, 28, 32, 36, 40, 44, 48 and 12-week follow-up.

- Change in symptom scores (assessed using Lower Respiratory Tract Infections – Visual Analogue Scale (LRTI-VAS) and Quality of Life Questionnaire– Bronchiectasis (QOL-B) from Baseline to Weeks 4, 8, 12, 16, 20, 24, 32, 40, 48 and 12-week follow-up.
- Change in Global Rating of Health (GRH) from Baseline to Weeks 4, 8, 12, 16, 20, 24, 32, 40, 48 and 12-week follow-up.
- Change in body weight from Baseline to Weeks 4, 8, 12, 16, 20, 24, 32, 40, 48 and 12-week follow-up.
- Change in 6MWD, oxygen desaturation and Borg CR10 scores during a 6MWT from Baseline to Week 12, 24, 48 and 12-week follow-up.

### **7.3.2. Safety Endpoints**

- Number of AEs, SAEs, ADRs, severe AEs and AEs leading to treatment discontinuation during the trial period.
- Change in WBC and differentials in blood from Baseline to Weeks 4, 12 24, 32, 40, 48 and 12-week follow-up.
- Change in DLCO from Baseline to Weeks 4, 8, 12, 16, 20, 24, 32, 40, 48 and at 12-week follow-up.
- Change in forced expiratory volume in 1 second (FEV1) (% predicted) and forced vital capacity (FVC) (% predicted) from Baseline to Weeks 12, 24, 32, 40 and 48.
- Development of anti GM-CSF antibodies at Week 4, 12, 24, 32, 48 and at 12-week follow-up.

## 8. INVESTIGATIONAL PLAN

### 8.1. Overall Trial Design

This is an open-label, non-controlled, multicenter, pilot clinical trial of inhaled molgramostim in subjects with persistent pulmonary NTM infection.

The primary objective is to investigate efficacy of inhaled molgramostim on NTM sputum culture conversion to negative. The primary endpoint is sputum culture conversion defined as at least three consecutive negative sputum samples during the treatment period.

Secondary objectives are to investigate the efficacy of inhaled molgramostim on NTM sputum smear conversion to negative, on reduction of NTM bacterial load in sputum and on Patient Reported Outcomes, exercise capacity as well as evaluation of the safety of inhaled molgramostim in these subjects.

Secondary efficacy endpoints and the safety endpoints are detailed in Section 7.3.

The study will comprise a Screening Visit, Baseline Visit, a 48-week treatment period and a 12-week follow up period. The Screening Visit (Visit 1) will be conducted up to 10 weeks prior to the Baseline Visit (Visit 2) to determine eligibility. Adult subjects with a history of chronic NTM infection with at least 2 positive cultures in the prior two years, of which at least one is within the last 6 months prior to Screening, will be considered for enrollment. Subjects should provide a positive NTM sputum culture at Screening to be eligible.

Two subgroups of subjects will be recruited:

- Group 1: Subjects who remain sputum culture positive while currently on a multidrug NTM guideline based antimycobacterial regimen, which has been ongoing for at least 6 months prior to the Baseline Visit.
- Group 2: Subjects who remain sputum culture positive but have either stopped a multidrug NTM guideline based antimycobacterial regimen at least 28 days prior to Screening due to lack of response or intolerance, or never started such treatment.

The study will include 30 subjects.

The treatment period will consist of 14 trial visits (Screening, Baseline, and at Weeks 4, 8, 12, 16, 20, 24, 28, 32, 36, 40, 44, and 48; Visits 1-14) and a follow-up visit (Visit 15) 12 weeks after end of treatment. The visits at Weeks 28, 36 and 44 (Visits 9, 11 and 13) will include a telephone contact, all other visits will include a clinic visit.

At the Baseline Visit (Visit 2), eligible subjects will start treatment with inhaled molgramostim administered via the PARI eFlow nebulizer.

At each visit (Visits 1-15), sputum samples for staining and microscopy, and microbiological culture will be collected. If required, induced sputum may be obtained according to local standards. On the days of clinic visits (Visits 1, 2, 3, 4, 5, 6, 7, 8, 10, 12, 14 and 15), subjects will be asked to collect two additional sputum samples at home, preferably on the consecutive days after the site visit. On the days of the telephone contact visits (Visits 9, 11 and 13), three sputum samples will be collected at home, preferably on consecutive days.

Any AEs will also be collected at Baseline and all subsequent visits (Visits 2-15). At all clinic visits a pregnancy test/contraceptive check will be conducted, changes in concomitant medication, measurement of body weight and an assessment of DLCO will be performed. A computed tomography (CT) scan will be conducted at Baseline (Visit 2) if not performed within 6 months prior to Baseline. If DLCO drops by at least 20% at two consecutive visits the CT scan may be repeated. A CT scan can be performed after 48 weeks of treatment if this is a part of the local routine clinical practice.

A physical examination and an electrocardiogram (ECG) will be performed at Screening and Weeks 24 and 48 (Visits 1, 8 and 14) and vital signs will be collected at Screening, Baseline, and Weeks 4, 12, 24, 32, 40 and 48 (Visits 1, 2, 3, 5, 8, 10, 12 and 14). Spirometry will be conducted at Baseline and at Weeks 12, 24, 32, 40 and 48 (Visits 2, 5, 8, 10, 12 and 14). A 6MWT will be conducted at Baseline, at Weeks 12, 24 and 48 and at the 12-week follow-up visit (Visits 2, 5, 8, 14 and 15). Blood samples for safety laboratory testing will be taken at Screening, Baseline, and at Weeks 4, 12, 24, 32, 40, 48 and at the 12-week follow-up visit (Visits 1, 2, 3, 5, 8, 10, 12, 14, 15). Anti-GM-CSF will be assessed at Baseline, at Week 4, 12, 24, 32, 48 and at the 12-week follow-up visit (Visits 2, 3, 5, 8, 10, 14 and 15). Patient reported outcomes (QoL-B, LRTI-VAS and GRH) will be assessed at Baseline and at all post Baseline clinic visits (Visits 2, 3, 4, 5, 6, 7, 8, 10, 12, 14 and 15). For subjects having a chest X-ray during the study period as part of the routine local clinical practice, the results from the X-ray will be recorded.

Participating subjects will be encouraged to contact the clinic between visits if they experience adverse events (AEs), worsening of their condition or have any other concerns. If needed, unscheduled visits will be conducted at investigator's discretion.

A schedule of study assessments is available in [Table 1](#).

Treatment with inhaled molgramostim will be given at a dosage of 300 µg once daily for 48 weeks. All subjects in the trial initially consented to 24 weeks of treatment. All enrolled subjects continuing with 48 weeks of treatment will re-consent and follow the visits schedule as described above.

Subjects that do not wish to continue to 48 weeks of treatment will end treatment after 24 weeks (visit 8) and will attend the follow-up visit 12-weeks later as per the visit schedule outlined in Protocol Version 2.0 or 3.0.

Subjects who complete the initial 24-week treatment period prior to the approval of Protocol Version 4.0 will proceed to the 12 week follow up as per the visit schedule in Protocol Version 2.0 or 3.0. Once Protocol Version 4.0 is approved they will be asked to re consent and re-initiate treatment. This will occur at the next trial visit or at an unscheduled visit. These subjects will not receive the whole 48-week treatment. They will receive treatment for an additional 24 weeks minus the number of weeks that they have been in follow up.

Subjects that do not wish to re consent and re initiate treatment will stay in follow up and attend the follow-up visit as per the visit schedule outlined in Protocol Version 2.0 or 3.0.

At Baseline and at Weeks 4, 12, 24, 32 and 40 (Visits 2, 3, 5, 8, 10 and 12), dosing will take place in the clinic after blood sampling. A data review was conducted after the first 6 subjects had completed 12 weeks of treatment. If safety concerns or poor tolerability were identified in this review, the review committee might decide on less frequent dosing for subsequent subjects

in the study. The review was conducted on 16 September 2018 and concluded that there were no safety issues of significant concern and the dose was unchanged. In order to obtain more robust treatment responses it was decided to extend the treatment duration from 24 to 48 weeks. Any changes to the conduct of the study such as change of dose, dose regimen or duration will be documented in a protocol amendment.

During the study, subjects in Group 1 will continue use of antimycobacterial treatment. All changes in antimycobacterial treatment will be recorded, including reasons for each change. In case of worsening of NTM pulmonary disease, antimycobacterial treatment may be added or a dosage increase of antimycobacterial treatment may be applied as rescue treatment, according to investigator's discretion.

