### **8.1.1. Trial Period**

Estimated date first subject screened: Q1 2018

Estimated date last subject completed (24 weeks treatment period): Q4 2019

Estimated date last subject completed (follow-up period): Q1 2020

The duration of trial participation for each subject is approximately 60 to 70 weeks:

- Screening period for the subjects is up to 10 weeks
- Treatment period up to 48 weeks (+/- 7 days)
- Follow-up for 12 weeks (+/- 7 days)

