#### 13.1. Primary Endpoint

- Sputum culture conversion defined as at least three consecutive negative sputum samples during the treatment period.

The time of culture conversion is defined as the time the first of three consecutive negative samples was obtained.

Sputum culture conversion rates (number of patients who convert to negative out of the number per group) will be presented with 95% exact binomial confidence intervals.

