9.2 Variables

9.2.1 *Primary Endpoint Variables*

- Sputum culture conversion during the treatment period defined as all available samples from three consecutive visits to be negative
- The time of culture conversion: Defined as the time the first of three consecutive visits with 100% negative samples was obtained. Subjects with no conversion will be censored at the date of their last visit.

9.2.2 *Secondary Endpoint Variables*

- Sputum smear conversion: Defined as at least three consecutive visits with 100% negative AFB stained sputum smears on microscopy during the treatment period in subjects that were smear positive at Baseline.
- Durability of sputum culture conversion: Defined as conversion at or before Week 48 and culture still negative at 12-weeks follow-up (with no positives in between).
- Durability of sputum smear conversion: Defined as conversion at or before Week 48 and smear still negative at 12-weeks follow-up (with no positives in between).
- Change from baseline in semi-quantitative grade of number of NTM on microscopy of AFB stained sputum smears
- Change from baseline in semi-quantitative grade of sputum cultures (measured by time to positivity and exploratory quantitation of cultures)
- Change from baseline in symptom scores
 - Lower Respiratory Tract Infections – Visual Analogue Score (LRTI-VAS)
 - Quality of Life Questionnaire – Bronchiectasis (QOL-B)
- Change from baseline in Global Rating of Health (GRH)
- Change from baseline in body weight
- Change from baseline in 6MWD, oxygen desaturation and Borg CR10 scores

9.3 **Biostatistical methods**

9.3.1 *Primary Endpoint*

9.3.1.1 *Sputum Culture Conversion*

Sputum culture conversion data will be listed, including time of culture conversion.

Sputum culture conversion rates (number of subjects who convert to negative out of the number per group) will be presented with 95% exact binomial confidence intervals.

On the basis of the poor historical success rates of current standard therapy, a 30% response rate for the primary endpoint will be considered clinically relevant.

Time to culture conversion will be evaluated using Kaplan Meier estimates, with 95% confidence intervals.

9.3.1.2 *Sensitivity Analyses*

In a sensitivity analysis, culture conversion will be re-defined as requiring at least 2 samples are available from each of the three consecutive visits. Sputum culture conversion rates and time to culture conversion will be analysed as part of this sensitivity analysis.

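### The primary conversion rate has a window that differs by subject, and neither it nor the 30% mark is tied to a landmark week

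*Protocol*

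**What the plan says.** **Endpoint.** Protocol 13.1 has "Sputum culture conversion defined as at least three consecutive negative sputum samples during the treatment period". SAP 9.2.1 restates it by visit: "Sputum culture conversion during the treatment period defined as all available samples from three consecutive visits to be negative". Neither names a week.

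**Length of the treatment period.** Protocol 8.1 reports the change made after the data review: "In order to obtain more robust treatment responses it was decided to extend the treatment duration from 24 to 48 weeks". Protocol 8.1.1 gives only an upper limit: "Treatment period up to 48 weeks (+/- 7 days". Protocol 8.1, repeated in SAP 2.1, creates three courses:

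- 24 weeks only: "Subjects that do not wish to continue to 48 weeks of treatment will end treatment after 24 weeks (visit 8". Those who finished 24 weeks before Version 4.0 was approved and decline to restart are in the same position. Both have a follow-up visit 12 weeks later.
- Interrupted, for those who finished before that approval and restart: "They will receive treatment for an additional 24 weeks minus the number of weeks that they have been in follow up".
- Continuous 48 weeks: "All enrolled subjects continuing with 48 weeks of treatment will re-consent and follow the visits schedule as described above".

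**Analysis.** SAP 9.3.1.1 reports "Sputum culture conversion rates (number of subjects who convert to negative out of the number per group", with exact 95% intervals. SAP 3.1 adds a total, and SAP 4.1.1 puts all enrolled subjects in one set. The same SAP section calls a 30% response rate clinically relevant without saying by when. It also plans Kaplan-Meier estimates of time to conversion. SAP 9.2.1 dates conversion to the first of the three negative visits and censors non-converters at their last visit. The only sensitivity analysis changes the number of samples required per visit. SAP 6 counts those completing 24 and 48 weeks, and SAP 8.1.1 counts treatment breaks, but the conversion analysis uses neither count.

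**The concern.** A subject treated for 48 weeks has more opportunities to show three consecutive negative visits than one who stops at 24 weeks. A proportion that mixes the two moves with extension uptake as well as with the drug effect. Extension requires re-consent in an open-label trial, so uptake may itself be related to how the subject feels or responds.

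Protocol 6.3 says the pilot is meant to inform the next, randomized trial. That trial will presumably have a fixed duration, and a rate without a fixed window is hard to carry over to it. The same applies to reading the result against 30%: a given proportion means something different if most subjects had 24 weeks than if most had 48.

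**Working it through.** The plan has no figure to reproduce: 30 subjects and the 30% mark are both stated without a calculation. The only arithmetic in the documents is the duration rule for interrupted subjects. With a gap of w weeks, time on drug is 24 + (24 − w) = 48 − w, so 44, 40 or 36 weeks for gaps of 4, 8 or 12.

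**1. Opportunities to convert.** Visits are four weeks apart, so m post-baseline visits give m − 2 three-visit runs.
- 24 weeks: 6 visits, 4 runs, starting at Weeks 4 to 16.
- 48 weeks: 12 visits, 10 runs, starting at Weeks 4 to 40.

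**2. Effect on the pooled proportion.** Assume a constant chance h per run and 30% conversion by Week 48 in a continuously treated subject.
- h = 1 − 0.70^(1/10) = 0.0350
- 24-week-only subject: 1 − (1 − h)^4 = 13.3%
- Pooled rate with share f on 24 weeks only and the rest on 48: 0.30(1 − f) + 0.133f

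The documents give no shares, so f is shown as a range. Interrupted subjects are left out because their gap lengths are unknown.

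| Share with 24 weeks only | Pooled rate |
|---|---|
| 10% | 28.3% |
| 20% | 26.7% |
| 33% | 24.5% |
| 50% | 21.6% |

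A hazard constant in calendar time gives 1 − 0.70^(1/2) = 16.3% for a 24-week-only subject, and pooled rates of 26.6% and 23.2% at shares of 25% and 50%. The picture is similar.

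**3. What Kaplan-Meier supplies.** Conversion is dated to the first negative visit of the run. Three negative visits by Week 24 (Weeks 16, 20 and 24 at the latest) therefore means onset by Week 16. Up to that point all three courses share one schedule, and the estimate at Week 16 equals the Week 24 proportion apart from early loss. In the model it is 13.3% at every share.

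After Week 16 a 24-week-only subject can have no event. Censored at the follow-up visit, such a subject still counts as at risk from Week 20 to about Week 36. Running the estimator under the same model, with a true 48-week rate of 30%:

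| Share with 24 weeks only | Kaplan-Meier at Week 40 onset, censored at last visit | Same, censored at last feasible onset |
|---|---|---|
| 10% | 28.6% | 30.0% |
| 20% | 27.3% | 30.0% |
| 33% | 25.5% | 30.0% |
| 50% | 23.2% | 30.0% |

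A reading at Week 24 on the onset axis is already low: at a 50% share it is 16.3% against a true 1 − (1 − h)^6 = 19.3%.

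**4. Scale.** The exact (Clopper-Pearson) 95% interval for 9/30 is 14.7% to 49.4%.

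**The case against.** The strongest reply is that the SAP already puts every subject on one time axis. Kaplan-Meier estimates with intervals are planned, conversion times are listed, and with 30 subjects the Week 24 count could be read from the listing. This stands as far as onset Week 16, where last-visit censoring does no harm. It does not stand beyond that, as step 3 shows, and the SAP names no week at which the curve is to be read.

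A reader might infer that the endpoint has no defined window and that no common-window rate can be obtained. The documents do not support that. The window is the treatment period, capped at 48 weeks, and the Kaplan-Meier curve contains one valid common-window rate. What is missing is a landmark.

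Three further replies have weight. The trial is a descriptive pilot without a hypothesis test, and 30% is a mark of relevance, not a decision rule. At shares of 10% to 20% the pooled rate moves by 1.7 to 3.3 points, far less than the sampling error. In this model the mixing lowers the rate, which is conservative against 30%. These limit the importance of the point. They do not supply a fixed-window figure for planning.

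It is also tempting to cite chance runs: with independent visits and an assumed 30% chance that a visit is negative, at least one run of three occurs in 8.4% of subjects over 6 visits and 18.9% over 12. That compares two schedules and would apply equally if everyone had 48 weeks. It shows why duration matters, not that pooling inflates the rate.

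**Conclusion.** The point holds in a limited form. The primary proportion, per group and in total, has a subject-dependent window of 24, 48 − w or 48 weeks, and neither it nor the 30% mark is tied to a week. Kaplan-Meier is a partial remedy: sound at onset Week 16 but not named there, and biased downward later under the stated censoring rule.

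Under the constant-chance assumption with 30% by Week 48, the pooled rate falls to between 28.3% and 21.6% as the 24-week-only share rises from 10% to 50%. The actual distortion cannot be computed because the shares are not given. If those who extend differ in prognosis from those who stop, the direction could also change, and corrected censoring would not cure that selection.

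It would go too far to say that the results cannot be used for planning. With a landmark named and the censoring corrected, they can. The change is worth making before analysis because it is specific and needs no new data.

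**What to change.** In SAP 9.3.1.1:

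1. Beside the existing rate, add the proportion of subjects with all three negative visits at or before Week 24 (onset by Week 16), for every subject, by group and overall, with exact 95% intervals.
2. In the Kaplan-Meier analysis, censor non-converters no later than the last on-treatment visit at which a three-visit run could still start and be confirmed: Week 16 for a completed 24-week course, Week 40 for a continuous 48-week course. Name the weeks at which estimates will be tabulated, and state how visits during a treatment gap count.
3. Show conversion counts by treatment course (24 weeks only, interrupted, continuous 48 weeks) descriptively, without intervals or comparison. The course is self-selected, and three courses by two groups among 30 subjects is six cells averaging five.
4. State which week the 30% mark refers to.

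The cost is one more set of rows in the primary table, a changed censoring date and a small count table. The downside is that the Week 24 rate will in general be lower than the headline rate, and both will have to be explained.
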